Study Protocol

Title: Heart rate and Breathing Effects on Attention and Memory (HeartBEAM)

NCT number: NCT05602220

IRB approval date: 5/15/2023

Uploaded date: 12/08/2025

Research Background

As we age, the parasympathetic system declines as the sympathetic system becomes hyperactive. In our previous clinical trial (Nashiro et al., 2023; Yoo et al., 2023), we found that increasing parasympathetic activity through daily practice of slow-paced breathing significantly decreased plasma amyloid- β (A β) in healthy younger and older adults (Min et al., 2023). In healthy adults, higher plasma A β is associated with greater risk of Alzheimer's disease (AD). Our primary goal of the current trial is to extend our initial findings regarding effects of slow-paced breathing on A β . Our secondary objectives are to examine the effects of daily slow-paced breathing on brain structure and the rate of learning.

Research Objectives

The aim of the study is to examine how daily paced breathing affects plasma A β levels and the rate of learning in older adults. Healthy adults aged 50-70 who meet all eligibility criteria will be invited to this study. Participants will be randomly assigned to one of the two conditions: 1) Daily memory and attention training followed by a paced breathing protocol designed to increase relaxation or 2) Daily memory and attention training followed by a paced breathing protocol to increase alertness. Participants will be asked to complete pre and post intervention cognitive testing online, engage in 10 weeks of daily brain training (starting Week 2) and 9 weeks of paced breathing (starting Week 3) at home. They will also be asked to come in for lab visits on Weeks 2, 7 and 12 to provide blood and urine samples to assess amyloid beta levels and to complete magnetic resonance imaging scans to assess perivascular space volume.

Methods and Design

Overview of the study

Timeline	Lab Visit	Home Tasks
Week 1		online consent, home cognitive testing
Week 2	(Visit 1) EEG tasks, questionnaires (Visit 2) MRI, blood & urine samples, cognitive tasks, questionnaires, give heart rate monitoring device	(Training Week 1) cognitive training + resting pulse measures (~40 min/day)
Week 3		(Training Week 2) cognitive + breathing training (~60 min/day)
Week 4		(Training Week 3) cognitive + breathing training (~60 min/day)
Week 5		(Training Week 4) cognitive + breathing training (~60 min/day)
Week 6		(Training Week 5) cognitive + breathing training (~60 min/day)

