After the second lab visit, participants will be asked to start an intervention, which involves doing 15-30 minutes of cognitive training and 30 minutes of paced breathing practice each day. In the first week of intervention, participants will be asked to do cognitive training only followed by measuring their resting heart rate. From the second week, they will be asked to do both cognitive training and paced breathing practice (with heart rate monitoring via an ear clip) each day. Participants will be randomly assigned to one of two conditions.

Condition 1: Slow-paced breathing condition (a paced breathing protocol designed to increase relaxation)

Each day, participants will be guided to do slow paced breathing at paces between 10-15 seconds per breath. Participants will receive continuous biofeedback in the form of a

score that is higher the **more** that their heart rate shows strong oscillatory activity at a slow breathing frequency. This is described as the 'relaxation' condition to participants.

Condition 2: Random-paced breathing condition (a paced breathing protocol to increase alertness)

Each day, participants will be guided to do random-paced breathing at paces between 4-6 seconds per breath. Participants will receive continuous biofeedback in the form of a score that is higher the **less** that their heart rate shows strong oscillatory activity at a slow breathing frequency. This is described as the 'alertness' condition to participants.

Participants in both conditions will also play Lumosity cognitive training games daily. Lumosity games are commercial cognitive training games designed to improve various core cognitive skills including memory, attention, processing speed, spatial orientation, mental flexibility, reasoning, and problem-solving skills (<https://www.lumosity.com/en/brain-games/>).

Lumosity provides a platform for researchers who aim to better understand human cognition. They agreed to provide services to our research team. Our liaison at Lumosity, [name], has consulted with us on some study design decisions but will not be involved in the collection or analysis of the data. In addition, Lumosity will not have access to identifiable data and will make the data collected on their platform available to us, as described below:

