During the intervention, each participant's progress will be facilitated by the app that will send reminders when they fail to complete practices. Progress will be monitored by a group of researchers; if participants fall behind on practice, we will contact them by email, phone, or video calls (e.g., Zoom) for us to check if they have any problems with any aspects of the study, such as device and internet issues. There will be no opportunities to make up sessions and if participants only complete part of a session one day, they will start at the beginning of a session the next time they practice. We anticipate high compliance with practice, as in our prior 5-week HRV biofeedback study, older participants averaged **over 100%** of the practice we asked them to complete (and by week 3, this was 40 min/day of biofeedback). In that study, we did not ask them to do more than 40 min/day so this is an indicator that they enjoyed it or felt they were getting something worthwhile from it. Thus, we have some experience indicating that the HRV-biofeedback is something that participants can do every day. In addition, Lumosity is a highly engaging platform and we anticipate that older adults will enjoy the activity.

Week 7 - Lab Visit 3 (around 2 hours):

Participants will be asked to complete the same assessments as in Visit 2 (i.e., MRI, blood draw, urine collection, blood pressure measurement, questionnaires).

Week 12 - Lab Visit 4 (around 2 hours):

Participants will be asked to complete the same assessments as in Visit 1 except that we will not repeat the following cognitive tests: MINT, FAQ and MoCA.

Week 12 - Lab Visit 5 (around 2 hours)

Participants will be asked to complete the same assessments as in Visit 2. They will also be asked to return their devices.

A few days after Visit 2, 3, and 5, participants will be asked to complete the post blood draw questionnaire to report any adverse events associated with the blood draw, if any. We will report to the IRB if the responses to any of the questions were the most negative response option. For example, one of the questions is “do you notice any bleeding after your session (on your way home or at home)? The response options are 1) no bleeding, 2) a little (perhaps a few drops, 3) yes (needed a new bandage). We will report to the IRB when the response was #3.

Week 12 - Home Tasks:

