- **Change in plasma amyloid beta levels:** We computed an aggregate score based on plasma A β 40 and A β 42 levels (pg/mL), calculated as the average of their Z-scores. Higher values on this composite measure are associated with greater risk of Alzheimer's disease. This score was compared across three time points: Week 2 (pre-intervention), Week 7 (mid-intervention), and Week 12 (post-intervention). We conducted a time (Week 2, 7, 12) \times condition ANOVA to test for a time \times condition interaction in plasma A β levels, assessing group differences in change over time.
- **Change in plasma Ab42/40 ratio:** The plasma A β 42/40 ratio was calculated by dividing the plasma A β 42 concentration (pg/mL) by the plasma A β 40 concentration (pg/mL) at each time point. We conducted a time (Week 2, 7, 12) \times condition ANOVA to test for an interaction effect, using plasma A β 42/40 ratio scores as the dependent variable to assess group differences over time.

Secondary outcome measures

- **Change in brain perivascular space (pvs) volume:** PVS volume was defined as the percentage of PVS volume relative to white matter volume in the centrum semiovale, our main region of interest. To examine condition differences in changes over time, we conducted a time (Week 2, 7, 12) \times condition ANOVA to test for an interaction effect.

- **Change in hippocampal volume:** We tested whether there were condition differences in changes in hippocampal volume. We performed a two-way mixed ANCOVA on hippocampal volume, with condition (slow-paced vs. random-paced) as the between-subjects factor and time point (Week 2, 7, 12) as the within-subjects factor, controlling for intracranial volume as a covariate.
- **Brain training performance on 12 Lumosity games during the breathing intervention (controlling for brain training performance pre intervention):** Increments in game play performance over the course of the intervention were captured on latent level, with all games contributing to the latent variable. To evaluate longitudinal changes in cognitive performance during the intervention, we fitted a linear mixed-effects model to participants' latent performance scores across the 10 time bins. We examined condition differences in performance changes over time.

Other pre-specified outcome measures

- Change in plasma pTau-181/tau ratio:
- Change in urine Ab42

Safety outcomes

Six non-serious adverse events were reported and subsequently resolved.

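### Does the Lumosity learning model need changing because the SAP does not state its random effects?

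*SAP*

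**What the plan says.** SAP section 3, under the secondary outcomes, names the measure as performance on 12 Lumosity games "during the breathing intervention (controlling for brain training performance pre intervention"). A latent score is built from all the games, a linear mixed-effects model is fitted to "latent performance scores across the 10 time bins", and the contrast is given in one sentence: "We examined condition differences in performance changes over time". Nothing is said about random effects, residual covariance, what a bin is, whether time is linear or categorical, or how pre-intervention performance enters. The hippocampal entry just above is fuller: it names its covariate and between-subjects factor, and gives "time point (Week 2, 7, 12) as the within-subjects factor".

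The Protocol's Research Objectives state the aim as the effect of paced breathing on plasma amyloid "levels and the rate of learning in older adults". Its Research Background makes amyloid the primary goal and places learning rate among the secondary objectives. The timeline has ten training weeks. The first comes before breathing starts ("Training Week 1) cognitive training + resting pulse measures"), and breathing fills the other nine.

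**The concern.** For a group difference in slope, the random effects decide where the error term comes from. With 62 participants and 10 bins, a random intercept alone takes it from bin-to-bin scatter within people, on 62 × 9 − 2 = 556 degrees of freedom. A random slope takes it from differences between participants' slopes, on 62 − 2 = 60. If people learn at different rates, or if neighbouring weeks are more alike than distant ones, the first error term is too small.

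Both are plausible for a learning curve. The daily schedule is "15-30 minutes of cognitive training and 30 minutes of paced breathing practice each day", and "There will be no opportunities to make up sessions", so the amount of practice behind each bin can differ between people. No other SAP analysis addresses learning rate. At stake is a false claim of a training benefit, made well above the nominal 5% rate, from a model the SAP's words would permit. Time coding also matters to the estimate: a lasting 0.3 SD step from bin 2 appears as about half that under a linear trend.

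**Working it through.** **The plan's own figure.** The only power statement (SAP section 2) is for plasma amyloid: f = .2, correlation .7, three assessments, 95% power, N = 42. The noncentrality is λ = f²·N·m/(1 − ρ) = .04 × 42 × 3/.3 = 16.8 on 2 and 80 df, giving 95.9% power; N = 40 gives 94.9%. So 42 reproduces. It says nothing about the Lumosity model, and its .7 is not a correlation of game scores.

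**Inputs.** From the documents: 31 completers per arm and 10 bins. Assumed: complete data, one bin per training week, unit total variance unless stated, two-sided α = .05.

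**Formulae.** With centred time t = −4.5 … 4.5, Sxx = 82.5. For within-person covariance R:

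- true variance of a person's slope: V = t′Rt/Sxx²
- variance implied by a random-intercept fit: W = σ²/Sxx, where σ² = [62·tr(CR) − 2·V·Sxx]/556 and C is the centring matrix
- false-positive rate: 2[1 − Φ(1.964/√(V/W))], where 1.964 is the critical t on 556 df

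**Serial correlation, r = .7.** V = .02594 and W = .00781, so V/W = 3.32. The true standard error is √3.32 = 1.82 times the reported one. Then 1.964/1.82 = 1.08, and the two-sided tail is 28.1%.

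**Equal correlation.** V = (1 − r)/Sxx and σ² = (1 − r)(558 − 2)/556 = 1 − r, so V/W = 1 and the rate is 5%.

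**Participants' own slopes.** Take residual variance .3 and intercept variance .7, with slope variance added on top. At slope reliability .5 the slope variance is .3/82.5 = .003636, so V = .007273. With σ² = [62 × (2.7 + .3) − 2 × .6]/556 = .3324, W = .004029, the ratio is 1.81 and the rate 14.4%.

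| Assumed structure | V/W | Random intercept, linear time |
|---|---|---|
| Equal correlation | 1.00 | 5% |
| Own slopes, reliability .2 / .5 / .8 | 1.22 / 1.81 / 3.49 | 7.5 / 14.4 / 29.3% |
| AR(1), r = .3 / .5 | 1.64 / 2.32 | 12.5 / 19.7% |
| Half stable, quarter AR(1), quarter noise, r = .7 / .9 | 1.91 / 1.86 | 15.5 / 15.0% |
| 70% AR(1), 30% noise, r = .7 / .9 | 2.39 / 2.54 | 20.4 / 21.7% |
| AR(1), r = .7 / .8 / .9 | 3.32 / 3.98 / 4.74 | 28.1 / 32.5 / 36.7% |

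Simulation (20,000 trials per setting) gave 27.7, 32.2 and 36.9% for the last row. REML fits (300 trials each) gave 27.0% at r = .7 and 34.3% at r = .9. With nine bins the last row runs from 26.7% to 34.4%. With time as a 10-level factor and a random intercept, the simulated rate is about 10 to 12% for that row and 5 to 8% for own slopes.

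**The sensible filling.** Comparing the 31 and 31 participant slopes, which corresponds to a random slope in balanced data, rejected about 5% in every setting. If the weeks really are equally correlated, it costs about one point of power: for a steady rise to 0.3 SD, 58, 76 and 97% become 57, 75 and 96% at r = .7, .8 and .9.

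**Time coding.** For a 0.3 SD step from bin 2, the centred times of bins 2 to 10 sum to 4.5. The fitted slope is 0.3 × 4.5/82.5 = .0164 per bin, or 9 × .0164 = .147 SD over the period, against 0.3 SD when each bin is compared with bin 1.

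**The case for a change.** The strongest case for acting is that the omission is real, nothing is redacted there, and the SAP gives such detail for hippocampal volume. Equal correlation, the one structure tried that is harmless, would need everyone to learn at the same rate and adjacent weeks to be no more alike than distant ones. Milder departures still inflate the rate to between 7.5% and about 22%. A sentence of text would be cheap, and the SAP is marked as a draft.

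Much of that stands: the description is incomplete, and a random-intercept-only fit with linear time would be hard to defend. What does not stand is the step from an incomplete description to a faulty analysis. The 28 to 37% range needs three things together: an analyst who omits the slope, linear time, and strong serial correlation with no bin-specific noise. The documents give none of them. The argument they do support, uneven practice, leads to the own-slopes rows. Even there the Protocol expects high compliance, with app reminders and staff contact for those who fall behind.

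How pre-intervention performance enters is open, but the intention is not, since the outcome's name calls for that control. Ten bins match ten training weeks, so bin 1 may well be the week before breathing starts, though this is unconfirmed. Using that week as the reference level or as a covariate would both honour the name.

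**Conclusion.** No change to the plan is needed. A linear mixed-effects model with a random intercept and slope meets the SAP's wording exactly and holds its error rate near 5% under every structure tried. It is an ordinary choice when the question is whether groups differ in rate of change. Nothing in the documents shows that a weaker model was fitted. The SAP is written in the past tense after 62 people had completed, so more wording would record what was done and would not prevent an error.

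The possible effect is bounded: one secondary outcome, with a false-positive rate between 5% and about 37% if a random intercept alone was used with linear time, and about 5% otherwise. Those figures rest on assumed correlation structures, complete data and weekly bins. The primary amyloid analyses and N = 42 are unaffected.

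The practical residue is a reading note. If the results report only a random intercept with linear time, the condition-by-time p-value should be treated with caution, since under AR(1) at .7 to .9 the honest standard error would be 1.8 to 2.2 times larger.

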Week 7	(Visit 3) MRI, blood & urine samples, questionnaires	(Training Week 6) cognitive + breathing training (~60 min/day)
Week 8		(Training Week 7) cognitive + breathing training (~60 min/day)
Week 9		(Training Week 8) cognitive + breathing training (~60 min/day)
Week 10		(Training Week 9) cognitive + breathing training (~60 min/day)
Week 11		(Training Week 10) cognitive + breathing training (~60 min/day)
Week 12	(Visit 4) EEG task, questionnaires (Visit 5) MRI, blood & urine samples, cognitive tasks, questionnaires, return heart rate monitoring device	home cognitive testing

Week 1 - Home Tasks:

After signing the consent form, participants will be asked to complete questionnaires and cognitive tasks online. We will email them a link to a website (custom programmed) that will administer a combination of the tasks listed below daily for a week. In the email, we will give them the following instructions: "Before you begin, please make sure all distractions are removed (i.e. TV, radio, phone and tablets are all turned off). While you complete the tasks, please do not eat, snack or drink; please do not leave your screen throughout the experiment (and if you have to, try to do it after you finish the task at hand); please wear glasses if needed." Participants' email will be their username and, on the first day, they will create a password for the website app that administers the tasks and questionnaires, which will take about 45 minutes each day. The information in parentheses below indicates domains of the tasks.

- 1) N-back task (memory)
- 2) Verbal learning memory task (memory)
- 3) Face-name recognition task (memory)
- 4) Pattern separation task (memory)
- 5) Task switching task (executive function)
- 6) Flanker task (executive function)
- 7) Stop-signal task (executive function)
- 8) Spatial orientation task (visuospatial function)
- 9) The Reading the Mind in the Eyes Test (emotion)
- 10) Profile of Mood States (emotion)
- 11) Verbal fluency task (language)
- 12) Daily Inventory of Stress Events (emotion)
- 13) Depression Anxiety Stress Scales – Short Form (emotion)
- 14) Positive and Negative Affect Schedule (emotion)
- 15) The Five Facet Mindfulness Questionnaire (emotion)
- 16) Physical activity ratings (physical activity; note that this questionnaire will be asked only at pre-intervention)
- 17) Epworth Sleepiness Scale (sleep)
- 18) Karolinska Sleepiness Scale (sleep)

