- 19) Memory for emotional state in the past week and prediction of mood for next week (memory)
- 20) Demographic information
- 21) Emotional memory task (emotion and memory)

If participants are unable to complete the cognitive/questionnaire module for a particular day, they will be asked to pick up that module of the study where they left off the next day. They can complete that leftover module and start and complete a new module the same day. However, they will not be allowed to start more than one module per day. If participants miss more than one out of 6 days of cognitive testing, they will be asked to leave the study.

Week 2 - Lab Visit 1 (around 2 hours):

Participants will be asked to complete the following cognitive tests and questionnaires at the Emotion & Cognition Lab:

- Trail Making Test (TMT)
- Animal fluency test
- Multilingual Naming Test (MINT)
- Functional Activities Questionnaire (FAQ)
- Montreal Cognitive Assessment (MoCA)
- Sleep questionnaire
- EEG tasks

Week 2 - Lab Visit 2 (around 2.5 hours):

The second visit includes the MRI assessments, which will take place at the USC Dana and David Dornsife Cognitive Neuroimaging Center (DNI). In the MRI session, the participant will be asked to simply rest (i.e., do nothing without falling asleep) during different types of scans. During the entire MRI session, their heart rate will be measured by a pulse oximeter. The total scan time will be an hour.

The rest of the visit will take place at the Emotion & Cognition Lab and the Psychology Department (SGM 906), which will take about an hour and half. Phlebotomists will collect blood samples up to 30 mL via venipuncture. Note that blood draw volume for blood donation in the US is 1 pint (~450 mL); thus, 30 mL should be safe for participants. Fasting is not required for the blood draw. Participants will also be asked to provide a urine sample (~20mL). Blood pressure will be measured by a blood pressure cuff. In addition, participants will be asked to complete the Profile of Mood States, the Daily Inventory of Stress Events, and the sleep questionnaire.

At the end of this visit, participants will receive their devices. The devices include a laptop with a customized paced breathing app, USB-module and a sensor that clips onto the earlobe and measures heart rate.

Week 2-12 (10-week intervention at home):

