Statistical Analysis Plan (SAP)

Study Title	Heart rate and Breathing Effects on Attention and Memory (HeartBEAM)
Principal Investigator	[name] Professor of Gerontology, Psychology and Biomedical Engineering University of Southern California Los Angeles, California, USA
Protocol identification number	UP-21-00357
ClinicalTrials.gov identifier	NCT05602220
Author	[name] Research Associate [name] of Southern California Los Angeles, California, USA
Version	Draft 0.1
Date	09/02/2025

1. Objectives and hypotheses

In our previous HRV-ER trial (NCT03458910), four weeks of daily slow-paced breathing designed to enhance parasympathetic activity reduced plasma A β levels in both younger and older adults. The current study aimed to extend those findings in adults aged 50 to 70 years using a 10-week intervention with three assessment time points. Secondary objectives included examining the effects of slow-paced breathing on brain structure (i.e., perivascular space and hippocampal volumes) and cognitive performance. We hypothesized that the 10-week slow-paced breathing intervention would reduce plasma A β levels and lead to improvements in brain structure and cognitive performance.

2. Sample Size & Power consideration

For plasma A β , we estimated reliability using correlations between pre- and post-intervention time points in the HRV-ER trial. Effect sizes were derived from the pre-post difference in the HRV-ER older adult Osc+ (slow-paced breathing) group. We powered the study to detect small-to-medium effect sizes ($f = .2$) with a .7 correlation among repeated measures and aimed for 95% power at $\alpha = .05$. Based on these parameters, a total sample size of $N = 42$ (with three assessments) was required. Sixty-two participants (31 in each condition) ultimately completed the study.

3. Outcome Measures and Analyses

We examined condition differences (slow-paced breathing vs. random-paced breathing) in intervention-related change in the following outcome measures. The average time between pre and post intervention assessment was 10 weeks.

Primary outcome measures

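### The SAP's only safety output is an unattributed total of six adverse events; a descriptive table by randomised condition and source should replace it

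*SAP*

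**What the plan says.** The Safety outcomes entry in SAP section 3 reads, in full: "Six non-serious adverse events were reported and subsequently resolved". No method, definition, event type, relatedness or safety population goes with it.

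The section opens with a general statement: "We examined condition differences (slow-paced breathing vs. random-paced breathing) in intervention-related change in the following outcome measures". Each primary and secondary outcome then has its own comparison by condition. The safety entry has none.

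SAP section 4 defines one analysis population: randomised participants who completed the assessments and whose data were good enough to analyse. Section 2 gives the only counts by arm: "Sixty-two participants (31 in each condition) ultimately completed the study". Neither document states how many were randomised.

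On design, the Protocol says "Participants will be randomly assigned to one of two conditions". The comparator is itself an active procedure, in which "participants will be guided to do random-paced breathing at paces between 4-6 seconds per breath", with its own biofeedback score. On capture of harms, the Protocol describes one route. A few days after Visits 2, 3 and 5, "participants will be asked to complete the post blood draw questionnaire to report any adverse events associated with the blood draw".

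**The concern.** The trial has no untreated arm, so the contrast between the two conditions is the only randomised evidence on tolerability that it can offer. A total without arms discards that contrast: the same sentence would be written whether the events were evenly spread or all in one condition.

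Three further gaps limit what the total can tell a reader.

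- **Events or people.** Six events could have occurred in as few as one participant or as many as six.
- **Denominator.** The only defined population is completers with usable data. The SAP does not say whether the six include events in people who withdrew.
- **Source.** The described questionnaire concerns venipuncture, which both arms undergo three times. The first draw, in Week 2, precedes the start of breathing practice in Week 3. If the six events came through that questionnaire, they would say little about breathing. If they came from breathing practice, the documents do not describe how they were collected.

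At stake is how well a reader can describe the tolerability of each condition. No efficacy result is affected.

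**Working it through.** The figure six is an observed count, so it cannot be re-derived. What can be checked is how much it leaves open.

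**Inputs**
- Events: 6 (SAP section 3, Safety outcomes).
- Completers: 31 per condition, 62 in all (SAP section 2). They stand in for the numbers assigned, which are not given.
- Assumption: at most one event per participant. The documents neither confirm nor exclude this.

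**Step 1: overall rate.** 6 / 62 = 9.7 events per 100 completers. Nothing further follows from the SAP sentence alone.

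**Step 2: every possible split.** For *a* affected in one arm and 6 − *a* in the other, the difference is *a*/31 − (6 − *a*)/31. The probability of a split, with the total fixed at six, is C(31, *a*) × C(31, 6 − *a*) / C(62, 6), where C(62, 6) = 61,474,519.

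- 6-0: 736,281 × 1 / 61,474,519 = 0.0120
- 5-1: 169,911 × 31 / 61,474,519 = 0.0857
- 4-2: 31,465 × 465 / 61,474,519 = 0.2380
- 3-3: 4,495 × 4,495 / 61,474,519 = 0.3287

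The two-sided Fisher value adds the probabilities of all splits at least as extreme, in both directions. For 6-0 it is 2 × 0.0120 = 0.024. For 5-1 it is 2 × (0.0120 + 0.0857) = 0.195. For 4-2 it is 2 × (0.0120 + 0.0857 + 0.2380) = 0.67.

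The intervals are Newcombe's, built from the Wilson limits of each arm. For 6-0 the Wilson limits are 9.2% to 36.3% for 6/31 and 0% to 11.0% for 0/31. The lower limit is therefore 19.4 − √((19.4 − 9.2)² + 11.0²) = 4.4, and the upper limit is 19.4 + (36.3 − 19.4) = 36.3.

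| Split | Risks | Difference (points) | 95% CI | Fisher p |
|---|---|---|---|---|
| 3-3 | 9.7% v 9.7% | 0.0 | −16.5 to 16.5 | 1.00 |
| 4-2 | 12.9% v 6.5% | 6.5 | −9.8 to 23.1 | 0.67 |
| 5-1 | 16.1% v 3.2% | 12.9 | −2.9 to 29.6 | 0.20 |
| 6-0 | 19.4% v 0% | 19.4 | 4.4 to 36.3 | 0.024 |

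Each unequal split can run in either direction. The p-values only show how far apart the possible cases lie. They are no argument for testing: only the most extreme split falls below 0.05.

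**Step 3: source.** The Protocol's one described capture route covers the blood draw, while the SAP sentence names no source. Neither document therefore lets the six events be divided between the draw, breathing practice and anything else.

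**The case against.** The strongest objection is that little is at stake. The intervention is behavioural, the sentence already says that every event was non-serious and resolved, and safety is not a stated objective in either document. Six events cannot support a useful comparison, and if they arose from blood draws, a split by arm would say almost nothing about breathing. Most of this stands. It makes the point minor, and it is why source has to be part of the table. It does not justify leaving the arms out, since a description by arm needs no power.

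Three stronger readings are tempting, and the documents do not support them.

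- **That the SAP breaks its own commitment.** The opening of section 3 promises condition differences in intervention-related change. An event count is not a change score, so the missing split is an omission rather than a contradiction.
- **That the trial can say nothing about relative safety, or is hiding a harm.** What the total can conceal is the allocation of six resolved, non-serious events. Counts by arm may exist outside these documents, the SAP draws no comparative safety conclusion, and it does not call the total pooled. Pooling over both arms is only the natural reading.
- **That blood pressure or the depression, anxiety and stress scale should become safety endpoints.** The Protocol calls neither a safety measure. They are also not the only repeated measures that might show harm: mood, stress-event, affect and sleepiness scales are repeated, and inter-beat intervals are recorded during practice. Choosing two of these after the study has finished would be post hoc.

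**Conclusion.** The point holds as a minor reporting weakness. The SAP neither reports nor plans adverse events by randomised condition, and its one total lacks a participant count, a denominator and a source. On the illustrative basis of 31 completers per arm and one event per participant, the total is compatible with differences from 0 to 19.4 percentage points in either direction. With other denominators or repeated events in one person the figures would change, but the ambiguity would remain. A by-arm table would improve what can be described about each condition. It would not turn six events into a comparative safety conclusion.

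A related limit would remain after the fix: the documents describe no solicited collection of harms from breathing practice, and tabulating the recorded events cannot make up for that.

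**What to change.** Replace the sentence under Safety outcomes with a descriptive table, one column per randomised condition, giving:

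- the number of participants assigned, including those who withdrew, as the denominator;
- the number of adverse events, and the number of participants with at least one;
- both counts split by source: blood draw, breathing practice, other;
- withdrawals for adverse events, counted in the assigned condition.

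State how each kind of event was collected, keep the statement that all events were non-serious and resolved, label the table descriptive and make no formal test. If the source of an event was not recorded, the table should say so.

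The cost is a few lines of SAP text and one table. The SAP is labelled Draft 0.1, and the table should need no new data and leaves the efficacy analyses unchanged. The drawback is that the counts will be small and imprecise and could be over-read, which is why the descriptive label matters.
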